5.1.1.3 Respiratory Forced Vital Capacity

A MMRM model will be fitted to the change from baseline to weeks █ and █ in the mean of the repeat assessments at a visit in respiratory forced vital capacity (FVC). The model will be fitted and results presented as described in section 5.1.1.1.

The observed mean (of the three repeat assessments) of the FVC and the change from baseline over time will be summarised. In addition, the observed mean at [redacted] and [redacted] and the change from [redacted] to [redacted] in the above observed mean will also be summarised. The observed mean will also be presented using by subject line plots over time ([redacted] and [redacted]) by dose group. In addition, line plots will present the adjusted LS mean changes from baseline and SEs over time, as estimated by the MMRM model, by dose group for FVC. Raw mean changes from [redacted] to [redacted] will be presented on the same plot.

FVC data will be listed.

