### **Assessment of Muscle Functioning**

#### **10.2.1 10 metre walk/run test**

The 10 metre walk/run test is a performance measure used to assess walking speed in metres per second over a short distance. It can be used as an assessment of functional mobility. The test will be conducted according to the schedule of assessments (Table 1) and will be performed at the subject's preferred walking speed and then at the fastest speed possible. For each speed, 3 assessments will be completed with a rest period until the subject has recovered.

The subject walks without assistance for 12 metres while the time taken to walk from metre 1 to meter 11 is recorded. The timing starts and stops when the toes of the leading foot cross the 1 and 11 metre marks respectively. If assistive devices are needed, these can be used but must be documented and kept consistent for that subject throughout the study.

For the fastest speed possible, the assessor will document whether the subject was able to run, walk fast or walk for each assessment. Whether the subject is running is defined as both feet being off the floor at the same time. If the subject is not able/willing to perform the fastest speed possible for all 3 assessments, this will also be recorded.

Appendix A provides further information on the test including verbal instructions to give to the subject.

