#### **10.2.2 Computerised handgrip myometer measure of grip strength and relaxation time**

Handgrip myometry is used as a measure of myotonia and muscle strength and has been validated as a reliable measure in patients with myotonic dystrophy type 1 (Moxley *et al.*, 2007).

The force of concentration exerted on the handle of a handgrip dynamometer is measured in addition to the time of contraction and relaxation. A computer stores the force curves for analysis to calculate the force of contraction/grip strength (Kg) and the time taken for the hand to relax from 90% contracted to 5% contracted (seconds).

Each assessment session consists of two trials per hand, each with three squeezes (maximum voluntary isometric contraction) on the handgrip dynamometer. Sessions are performed in accordance with the schedule of assessments. Both hands will be assessed.

The tester will allow an adequate amount of time after the first squeeze for the force curve to return to and remain at the level at the beginning of the trial (approx. 20 seconds) prior to proceeding with the remaining two grip contractions within the trial. The subsequent two squeezes will be approximately 3 seconds of contraction followed by 10 seconds of relaxation. After the first trial (3 squeezes), the subject will rest that hand for approximately one minute. While one hand is recovering, the other hand can be tested.

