#### **10.2.3 Respiratory - FVC**

Forced Vital Capacity (FVC) is a measure of lung function which is obtained via spirometry. FVC is the total amount of air exhaled during a Forced Expiratory Volume (FEV) test using a spirometer. Measurements will be taken according to the schedule of assessments.

The subject should be sitting in a chair for the test. The evaluator will either explain or demonstrate the procedure to the subject and explain that they will be performing the test at least 3 times. The specific wording of instructions is detailed in Appendix B.

The test should be repeated at least 3 times, making sure that the subject has recovered between attempts. If at each attempt there is an improvement in the results, further tests can be conducted until the subject has achieved his/her best result.

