**17.2 Appendix B: Pulmonary Function Test Instructions**

### **Pulmonary Function test (FVC - SITTING)**

[figure not shown]
Forced Vital Capacity (FVC) will be performed in the sitting position.

The patient should be sitting comfortably in a chair. The evaluator explains /demonstrates the procedure to the subject and explains that they will be performing the test at least 3 times. The specific wording of instructions should be followed closely.

- Ask the patient to '*take as big a breath in as possible and then blow out through the mouth as hard and as long as you can*'. The evaluator should verbally encourage the subject to keep going for as long as possible. ATS criteria state a 6 second plateau is required.
- The test should be repeated three times making sure that the patient has recovered between attempts. If at each attempt there is an improvement in the results further tests can be conducted until the subject has achieved his best result.
- The subject can place the mouthpiece in his own mouth unless he is unable to reach his mouth with his hands or flexes his head and shoulders to reach the tube. In this case the evaluator should place the tube into the subject's mouth.
- The tube can be placed in the mouth either before the beginning of inspiration (closed circuit technique) or at the end of inspiration just prior to expiration (open circuit technique) whichever the subject finds most comfortable.
- Whichever technique is used the same method should be used at each evaluation and documented on the worksheets.
- A nose clip should be applied just prior to expiration. If a tight seal cannot be made around the tube then a mask may be used.
- The subject should not be allowed to flex forward during expiration.
- Calibrate the spirometry system on the day of testing

17.3 **Appendix C: Nine Hole Peg Test**

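### Does SAP 5.1.1.3 need a new per-visit FVC, given its two wordings of the mean and a test that can run on to a best blow?

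*SAP*

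**What the plan says.** SAP 5.1.1.3 fits the MMRM to the change from baseline in the "mean of the repeat assessments at a visit in respiratory forced vital capacity (FVC"). The next paragraph covers the tables: "The observed mean (of the three repeat assessments) of the FVC and the change from baseline over time will be summarised". The by-subject plots use that same observed mean. The LS mean figure comes from the MMRM, and on it "Raw mean changes from [redacted] to [redacted] will be presented on the same plot".

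Protocol 10.2.3 asks for at least three blows; Appendix B says three. Both add that, if every attempt improves on the last, "further tests can be conducted until the subject has achieved his/her best result". Appendix B also covers technique: "The evaluator should verbally encourage the subject to keep going for as long as possible" and "ATS criteria state a 6 second plateau is required". Neither document says that the best blow is the value to be analysed.

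The other repeated muscle tests have fixed counts. For the walk, "For each speed, 3 assessments will be completed with a rest period until the subject has recovered"; for grip, "Each assessment session consists of two trials per hand, each with three squeezes". SAP 5.1.1.1 and 5.1.1.2 average these repeats, although the fast walk and the grip squeeze are maximal-effort tests too.

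The FVC data are listed (SAP 5.1.1.3 and Listing 16.2.6.3). Cohort 1 FVC has already been modelled ad hoc from the 5.1.1.3 MMRM (SAP 3.1.1; Table 14.2.3.1_AH1 in Appendix 2).

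**The concern.** Of these three tests, only FVC has an open-ended number of repeats, and the subject's own rising results trigger the extra ones. If a fourth blow is recorded, the MMRM wording takes in all blows and the summary wording takes in three, without saying which three. The model output and the tables could then disagree, and one figure would carry both quantities.

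The second worry is the mean itself. If early blows are submaximal, averaging them in makes FVC sensitive to effort. The evaluator coaches each blow, the site knows the treatment (protocol 9.3), and there is no concurrent control. Better effort after baseline could then partly appear as an FVC gain. Taking the best blow looks like the natural remedy, since the test procedure works towards it.

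**Working it through.** The documents give no FVC data, so there is no plan figure to reproduce. The blow counts and the stopping rule come from protocol 10.2.3 and Appendix B. Everything else is assumed: true FVC 2.5 L, mean effort deficit 8% at baseline (exponential), blow noise SD 3% where stated, and extra blows only while every blow improves. Simulations used 400,000 sessions per visit.

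**1. When the wordings differ.**
- Three blows (2.0, 2.1, 2.2 L): both wordings give 2.10 L.
- Five rising blows (2.0 to 2.4 L in steps of 0.1): all blows 2.20 L, first three 2.10 L, last three 2.30 L, best 2.40 L.

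The gap therefore needs a fourth recorded blow. Extra blows are optional, and the eCRF layout is not shown.

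**2. How often a fourth blow is allowed.** With no trend, three blows are in rising order in 1 of 3! = 6 sessions (17%). With rises of 1% or 2% per blow and 3% noise, it is 27% or 40%.

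**3. Size of the gap (mean of all minus mean of first three).**
- No trend, 8% independent deficit: in sessions with more than three blows, 0.046 L in mean absolute size (95th percentile 0.14 L) and about 0 net. If 50% or 80% of the deficit is shared by all blows in a session, the absolute gap falls to 0.023 or 0.009 L.
- Rising 1% or 2% per blow, 3% noise: net +0.020 or +0.052 L in sessions with more than three blows. Over all sessions this is 0.27 × 0.020 = 0.005 L or 0.40 × 0.052 = 0.021 L.

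**4. What the best blow gains when effort changes.** Bias of the mean = 2.5 × fall in deficit. For the best of three, multiply by shared + (1 − shared)/3, because the smallest of three independent exponential deficits averages one third of their mean. The simulated values below include the extra blows.

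| Deficit | Mean (L) | Best, 0% shared | 50% | 80% | 100% |
|---|---|---|---|---|---|
| 8% to 8% | 0 | 0 | 0 | 0 | 0 |
| 8% to 6% | 0.050 | 0.016 | 0.033 | 0.043 | 0.050 |
| 8% to 5% | 0.075 | 0.024 | 0.049 | 0.065 | 0.075 |

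For the fall to 6%, the best blow removes 0.034, 0.017, 0.007 or 0 L.

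**5. What the best blow loses when the count changes.** Going from 3 to 5 blows with the deficit unchanged at 8% moves the best by 2.5 × 0.08 × (1 − shared) × (1/3 − 1/5) = 0.027, 0.013 or 0.005 L at 0%, 50% or 80% shared. The mean of the first three moves by 0. This loss is of the same order as the gain in step 4.

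**6. Noise and practice.** Take symmetric blow noise of 3% × 2.5 = 0.075 L.
- No trend: SD of change 0.060 L for the mean and 0.079 L for the best. As a check, exactly three blows give 0.075 × √(2/3) = 0.061 L for the mean.
- Blows rising 2% each to a plateau at the fifth, at both visits: 0.067 L against 0.110 L.
- The same rise at baseline, flat blows later, true capacity unchanged: spurious change 0.132 L for the mean and 0.109 L for the best. The best removes 0.023 L, or 0.023/0.132 = 17%, because most sessions still stop at three blows, before the plateau.

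**The case for a change.** The strongest case for a change is a noise-free one. Suppose a subject's best is 2.40 L at both visits, reached in five rising blows at baseline and three at the end of treatment, in steps of 0.1 L. The mean of all blows then rises from 2.20 to 2.30 L, a spurious +0.10 L. The mean of the first three rises from 2.10 to 2.30 L, or +0.20 L. The best blow shows no change. On this view, effort-resistant measurement is worth having in an uncontrolled study, and even those who prefer the mean must say which blows enter it.

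Part of this stands. The two wordings exist, rising blows give the gap a direction, and one set of blows has to be chosen. But the example assumes that the subject reaches the same maximum each time with no blow-to-blow noise; step 6 shows how little of the advantage remains with 3% noise. Coaching and knowledge of treatment also tend to act on the whole session. That is the mostly shared case, where the best blow gains little or nothing. Offering extra blows is at the discretion of the same unblinded site, so the maximum is open to the same worry.

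**Conclusion.** No change to the plan is needed. The difference in wording is a small drafting gap. Both sentences describe the mean of the repeats at a visit, and the word three matches Appendix B. Analysts who derive one FVC value per visit will choose one set of blows and use it for model, tables and plots. Left unsettled, the gap would be about 0.02 to 0.05 L in sessions that ran on with rising blows, and about 0.005 to 0.021 L over all sessions, under assumed rises of 1% to 2% on 2.5 L. With exactly three recorded blows it is zero.

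Mean or best blow is a fair choice either way. Neither document names the maximum as the endpoint, and averaging is what the SAP does for grip and the fast walk. The gain ranges from threefold to nil, the blow-count risk is of similar size, and the SD of change is larger under symmetric noise. A switch now would also come after Cohort 1 FVC results had been reviewed, which disclosure would not fully cure.

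Drift before baseline is already visible in the run-in summaries (protocol 11.5) and in the raw changes plotted beside the LS means. Effort change after baseline is not, but that limits every effort-dependent endpoint here. All sizes rest on assumed inputs. FVC is one of many secondary endpoints in a study of 16 subjects with no power calculation, and the primary safety conclusion does not depend on it.

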5.1.1.4 Actigraphy

For each subject and visit, actigraphy data will be selected for analysis based on the following rules:

1. Take the first 7 consecutive days following the visit date (where Day 1 of the 7 days is the day after the visit date).
2. Exclude the first and last of these 7 days to leave 5 consecutive days.
3. Considering the remaining 5 days, exclude any day with less than 5 hours of wear time in total (this does not have to be consecutive hours).
4. Following the above steps, if less than 3 days remain, exclude all actigraphy data for this visit for the subject (visit is treated as missing and subject to the imputation methods outlined in this SAP for MMRM analyses)

Following application of the above rules, an assessment will be performed to determine how many subjects have non-missing data meeting the criteria at each of the visits (with particular reference to Baseline and [REDACTED] [REDACTED])

For each subject and visit, the measurements to be summarised and analysed will be 'Weekly total per hour of wear time'. This will be derived as the total value across all valid days for the visit (selected in steps 1-4 above) divided by the total hours wear time across these valid days. This calculation will be performed separately for

the weekly total number of steps per hour of wear time, weekly total number of 3 minute bouts of activity per hour of wear time, weekly total number of >10 minute bouts of activity per hour of wear time. A 3 minute bout of activity will consist of 3 minutes of activity, with zero minutes 'drop time' and 300 activity counts per minute.

The weekly total number of steps per hour wear time, total number of 3 minute bouts of activity per hour wear time, total number of >10 minute bouts of activity per hour wear time will be derived at each visit from [redacted] onwards.

Baseline will be taken from the 7 days of activity recorded commencing from the day after the [redacted] date. The Actigraph activity recorded during the 7 days following each visit, will be assigned to the next visit i.e. the actigraphy data recorded during the 7 days commencing the day after the [redacted] (week [redacted]) date will be assigned to [redacted] (week [redacted]) and so on.

A MMRM model will be fitted to the change from baseline to the above assigned weeks [redacted] in the weekly total number of 3 minute bouts of activity per hour wear time. The model will be fitted and results presented as described in section 5.1.1.2.

The observed weekly total: number of steps per hour wear time, number of 3 minute bouts of activity per hour wear time and number of >10 minute bouts of activity per hour wear time and the corresponding change from baseline will be summarised. The weekly totals per hour wear time will also be presented using by subject line plots over time (assigned [redacted] (baseline), assigned [redacted], assigned [redacted] and assigned [redacted] by dose group. In addition, line plots will present the adjusted LS mean changes from baseline and SEs over time, as estimated by the MMRM model, by dose group for the weekly total number of 3 minute bouts of activity per hour wear time.

Actigraphy data will be listed.

5.1.1.5 Nine Hole Peg Test

A MMRM model will be fitted to the change from baseline to weeks [redacted] in the time taken (seconds) to complete the nine hole peg test (NHPT) for the dominant arm. The model will be fitted and results presented as described in section 5.1.1.2.

The observed time taken to complete the NHPT and corresponding change from baseline over time will be summarised separately for the dominant and non-dominant arms. In addition, the time taken to complete the NHPT at [redacted] and [redacted] and the change from [redacted] to [redacted] will also be summarised separately for the dominant and non-dominant arms. The observed time taken will be presented using by subject line plots over time ([redacted], [redacted], [redacted] and [redacted]) by dose group separately for the dominant and non-dominant arms. In addition, line plots will present the adjusted LS mean changes from baseline and SEs over time, as estimated by the MMRM model, by dose group for the time taken to complete the NHPT for the dominant arm. Raw mean changes from [redacted] to [redacted] will be presented on the same plot.

NHPT data will be listed.

5.1.2 Clinician/Caregiver Symptom Scales

5.1.2.1 Clinical Global Impressions

An ANCOVA will be fitted to the change from baseline to end of treatment in the clinical global impression – severity of illness scale (CGI-S). The ANCOVA will include the baseline value as a covariate and dose group as a fixed effect. Adjusted LS Means for the dose group means at the end of treatment estimated by the above model will be presented, together with the associated SE, 95% CIs and 2-sided p-values.

CGI-S and change from baseline will be summarised over time using summary statistics. CGI-S at [redacted] and [redacted] and the change from [redacted] to [redacted] in CGI-S will also be summarised using summary statistics. In addition, line plots will present the adjusted LS mean changes from baseline to end of treatment and SEs, as estimated by the ANCOVA, by dose group for the CGI-S. Raw mean changes from [redacted] to [redacted] will be presented on the same plot.

A MMRM model will be fitted to the observed values at weeks [redacted] and [redacted] in the clinical global impression – improvement scale (CGI-I). The model will include dose group and visit as fixed effects, and the treatment-by-visit interaction. F-tests from PROC MIXED will be based on Kenward-Roger's adjusted degrees of freedom. The following variance/covariance matrix structures for the repeated visits within a subject will be assessed: Compound symmetry, 1st order autoregressive, Toeplitz and unstructured. The variance/covariance matrix structure that results in the smallest Akaike information criterion (AIC), indicating the best model fit will be selected. Adjusted LS Means for the dose group means at each visit estimated by the above model will be presented, together with the associated SE and 95% CIs. The 2-sided p-values will also be presented at each visit for the comparison of the adjusted LS Means to a CGI-I score of 4 (representing "No Change").

CGI-I observed values will be summarised over time using summary statistics. By subject line plots of the CGI-I results will be presented over time ([redacted], [redacted] and [redacted]) by dose group. In addition, line plots will present the adjusted LS means and associated SEs for the observed values over time, as estimated by the MMRM model, by dose group for the CGI-I.

The CGI-I and CGI-S data will be listed.

5.1.2.2 Clinician-completed Domain Specific Causes for Concern VAS: Myotonic Dystrophy

A MMRM model will be fitted to the change from baseline to weeks [redacted] and [redacted] in the total clinician-completed domain specific causes for concern VAS score. The model will be fitted and results presented as described in section 5.1.1.1.

The observed total clinician-completed domain specific causes for concern VAS score and domain specific VAS scores and corresponding change from baseline will be summarised over time. In addition, the above scores at [redacted] and [redacted] and the change from [redacted] to [redacted] will be summarised. The observed total clinician-completed domain specific causes for concern VAS score and domain specific VAS scores will also be presented over time ([redacted] and [redacted]) using by subject line plots by dose group. In addition, line plots will present the adjusted LS mean changes from baseline and SEs over time, as estimated by the MMRM model, by dose group for

the total clinician-completed domain specific causes for concern VAS score. Raw mean changes from [redacted] to [redacted] will be presented on the same plot.

The relationship between the change from baseline to week [redacted] in the total clinician-completed domain specific causes for concern VAS score and the change from baseline to week [redacted] in total lean muscle mass will be evaluated by plotting the change from baseline to week [redacted] in the total clinician-completed domain specific causes for concern VAS score against the change from baseline to week [redacted] in total lean muscle mass.

The clinician-completed domain specific causes for concern VAS data will be listed.

5.1.2.3 Top 3 Concerns Visual Analogue Scale (VAS)

The top 3 caregiver and subject concerns recorded for each subject will be mapped to the clinician-completed domain specific causes for concern.

A MMRM model will be fitted to the change from baseline to weeks [redacted] and [redacted] in the top 3 concerns VAS total score (derived as the total of the VAS scores for the three concerns) separately for the caregiver and subject. The model will be fitted and results presented as described in section 5.1.1.1.

The observed top 3 concerns VAS total score and corresponding change from baseline will be summarised over time separately for caregiver and subject. In addition, the above VAS scores at [redacted] and [redacted] and the change from [redacted] to [redacted] will be summarised. The observed top 3 concerns VAS total score will also be presented over time ([redacted] and [redacted]) using by subject line plots by dose group, separately for the caregiver and subject. In addition, line plots will present the adjusted LS mean changes from baseline and SEs over time, as estimated by the MMRM model, by dose group for the top 3 concerns VAS total score separately for the caregiver and subject. Raw mean changes from [redacted] to [redacted] will be presented on the same plot.

The top 3 concerns data, including the mapped domains and VAS scores will be listed. The listing will include change from baseline for the individual concerns VAS scores as well as the total VAS scores for each subject or caregiver.

